## **1. Protocol Synopsis**

### **1.1. Study Premise**

Pelvic floor physical therapy (PFPT) is a widely accepted treatment for many urogynecologic diagnoses, such as stress and urge urinary incontinence, pelvic organ prolapse, and myofascial pain of the levator ani muscles. This conservative treatment modality has virtually no risk, unlike medications or surgery. It is especially useful for patients who are otherwise poor surgical candidates. This treatment consists of weekly one hour long physical therapy sessions with therapists specially trained in the pelvic floor musculature. Treatment length depends on severity of symptoms and patient progress, but is usually anywhere from five to fifteen visits at our practice.

Many investigators worldwide have studied what factors influence patient compliance with this therapy. Some barriers that have been identified including being too busy with work, being afraid of vaginal palpation, feeling ashamed, feeling too old to engage in such therapy, or having symptoms that are minor. Another analysis found that age, distance from home, and diagnosis necessitating PFPT were factors in compliance. We have recently performed an IRB-approved retrospective chart review to determine PFPT compliance within our practice. We found that 66% of patients attended at least one therapy session. Of these women, 73% attended at least half of the recommended visits.

Our practice wants to develop an educational tool to improve PFPT compliance. We designed and created a four minute patient education video with assistance of the marketing department. This video includes physicians, pelvic floor physical therapists, and one of our patients speaking to the most common questions and concerns patients have. Now we aim to assess if patients who use this education tool will have improved compliance to therapy.

### **1.2. Specific Research Question**

Does viewing an educational video augment patient compliance with PFPT compared to standard counseling?

### **1.3. Study Objectives and Hypotheses**

Objective: To determine the impact on PFPT compliance in patients who view an educational compared to standard counseling

Hypothesis: Compared to patients receiving standard counseling, those who receive both the standard counseling and educational video intervention will

- 1) Be more likely to complete at least half of their recommended PT visits
- 2) Be more likely to initiate PFPT
- 3) Will have a shorter time to initiation of PFPT
- 4) Be more likely to discharge from PFPT
- 5) Will have greater improvement in urogenital distress following PFPT

#### **1.4. Summary of Study Design**

**Study Design:** Randomized controlled trial

**Population:** Clinic-based patients seen at the Loyola University Medical Center Urogynecology outpatient clinic who have been prescribed PFPT as a treatment for their condition and agree to such therapy.

**Control group:** Will read standard PFPT handout (see Appendix 4.1)

**Intervention group:** Will read standard PFPT handout plus watch education video (see Appendix 4.2)

**Study Length:** At least three months after the initial PFPT referral for each patient, medical record review will be performed to record therapy attendance, including date of first visit, number of visits recommended by the therapist, number of completed visits, and whether the patient was discharged from PFPT.

**Power-calculation:** One goal of the proposed study is to test the null hypothesis that the rate of women attending at least half of their required PT visits is identical in the two populations: Those assigned to handout only and those assigned to handout and video intervention. With proposed sample sizes of 96 assigned to handout only and 96 assigned to handout and video intervention, the study will have power of 80% to yield a statistically significant result.

This computation assumes that the difference in proportions of compliance is 20% (specifically, 70% versus 50% compliance for the intervention and control groups, respectively). It also assumes that the criterion for significance (alpha) will be set at 0.05 and that the test will be 2-tailed, meaning an effect in either direction will be interpreted.

This effect was selected as the smallest effect that would be important to detect, in the sense that any smaller effect would not be of clinical or substantive significance. It is also assumed that this effect size is reasonable, in the sense that an effect of this magnitude may be anticipated in this research.

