## **2. Protocol**

Patients who have been interviewed, examined, and a plan has been made by the treating physicians in the Female Pelvic Medicine & Reconstructive Surgery practice will be invited to participate at the end of the visit if the patient and physician mutually agree that PFPT is the treatment modality to pursue.

If she agrees to participate, she will be consented and randomized. If she is randomized to standard counseling, she will be given the standard handout to read. If she is randomized to the intervention, she will be both given the standard handout and then view the 4-minute educational video on a clinic iPad.

At the conclusion of the counseling, patients will be asked if they have any additional questions, and these will be recorded and answered. The patient will also fill out a visual analog scale about how informed she feels. (See appendix 4.3 & 4.4)

**Follow-up:** Patient chart will be monitored following enrollment in the study to measure time to PFPT attendance and PFPT compliance (See appendix 4.5).

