## **2.6. Statistical analysis**

Binary logistic regression will be used to compare the odds of PFPT initiation, PFPT discharge, completion of half of the recommended visits, and having any further questions after counseling between those assigned to the enhanced versus standard counseling groups. In these models, expected frequencies will be monitored and exact logistic regression models will be used when these values are sparse. We will also

stratify the comparison of PFPT initiation by participants' primary language. Because few patients will have Spanish as their primary language, we will make an *a-priori* decision to use an exact binary logistic regression model to compare the two treatment groups among Spanish speaking participants. Subsequently, a Breslow-day test may be used to compare the stratified English and Spanish speaking odds ratios for homogeneity.

A binary logistic regression model will also be used to estimate the odds of being discharged from PFPT as a function of the number of completed visits, and a Kaplan-Meier curve will be used to estimate the probability of not attending a PFPT visit following date of referral for those in the experimental and control cohorts. Using this approach, elapsed time will be measured in days from referral date to date of first visit for those who attended PFPT. Individuals who never attended PFPT will be censored at the last date they were known to be absent from therapy.

For each patient, the change in UDI-6 will be calculated by subtracting the post-treatment score from her pre-treatment score, and an independent samples *t*-test will be used to compare this change score between those assigned to the experimental group versus control group. In this model, normality and influential outliers will be assessed using QQ plots and box plots, respectively. A non-parametric Wilcoxon rank-sum test may be used if the data violate parametric assumptions. Finally, though a Kaplan-Meier method is primarily used to compare days from date of referral to date of first visit between the experimental and control groups, a Wilcoxon rank-sum test will also be used to make this comparison as a sensitivity analysis among those who attend PFPT. All analyses will be completed using SAS version 9.4 (Cary, NC).

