## Too much information

#### **4.5 Patient information collected (from EMR < nine months later)**

**Time to first PFPT visit from day of referral:** \_\_\_\_\_ days

**Physician who referred:**      [name]      [name]      [name]      [name]

**Number of recommended visits:** \_\_\_\_\_

**Number of completed visits:** \_\_\_\_\_

**Discharged from PFPT practice (circle):** yes      no

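### Half-completion and discharge have no common observation window, so an early chart review can score patients still in therapy as failures

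*Combined protocol and SAP*

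**What the plan says.** - **Timing of review.** Section 1.4, under study length: "At least three months after the initial PFPT referral for each patient, medical record review will be performed to record therapy attendance". No latest date is given there. Section 2 adds only this: "Patient chart will be monitored following enrollment in the study to measure time to PFPT attendance and PFPT compliance". The one upper limit is the heading of Appendix 4.5: "Patient information collected (from EMR < nine months later".
- **What is recorded.** Section 1.4 and form 4.5 list the first visit (as a date, or as days from referral), visits recommended, visits completed, and discharge as yes or no. Neither lists a review date, a last-visit date or a discharge date.
- **Analysis.** Section 2.6: "Binary logistic regression will be used to compare the odds of PFPT initiation, PFPT discharge, completion of half of the recommended visits". It states no time point, offset, follow-up covariate or censoring for these outcomes. Unequal follow-up is handled only in the Kaplan-Meier analysis of time to first visit: "Individuals who never attended PFPT will be censored at the last date they were known to be absent from therapy". Form 4.5 has no field for that date.
- **Length of therapy.** Section 1.1: "This treatment consists of weekly one hour long physical therapy sessions", and the course length "is usually anywhere from five to fifteen visits at our practice".
- **Expected effect on starting.** Section 1.3, hypothesis 3, for the video group: "Will have a shorter time to initiation of PFPT".

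**The concern.** Half-completion (hypothesis 1, and the basis of the sample size) and discharge (hypothesis 4) both accumulate over time. Their value depends on when the chart is opened. The plan lets that moment range from three months to just under nine, and the form does not record it. The same patient can be a failure at three months and a success at eight.

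Review dates that vary without regard to arm do not bias the comparison. The difficulty comes from hypothesis 3. If the video brings patients to therapy sooner, a review near the floor finds video patients further along. The video could then look better on hypotheses 1 and 4 although no more of its patients would eventually complete. Speed of starting, which has its own hypothesis, would be counted again as compliance. Even with equal waits, early review misses some true completers in both arms and costs power.

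**Working it through.** **1. The plan's own figure.** Inputs from section 1.4: 96 per arm, 70% v 50%, two-sided alpha 0.05.

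- Wald test of the log odds ratio, matching the planned model: n = (1.960 + 0.842)² × (1/0.25 + 1/0.21) / [ln(0.7/0.3)]² = 95.8, so 96 per arm, with power 80.1%.
- Test of two proportions: power = Φ{[0.2√96 − 1.96√(2 × 0.6 × 0.4)] / √(0.25 + 0.21)} = 81.2%.

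The stated 80% is reproduced. The sample-size arithmetic is not in question.

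**2. Width of the window.** Three months is about 13.0 weeks and nine months about 39.1 weeks, a threefold range.

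**3. Calendar arithmetic.** Inputs from section 1.1: weekly visits, R = 5 to 15. With no missed weeks, the last visit is 7(R − 1) days after the first, and half is ceil(R/2) visits. Latest start day after referral for a review at day 91:

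| R | To finish | To reach half |
|---|---|---|
| 5 | 91 − 28 = 63 | 91 − 14 = 77 |
| 10 | 91 − 63 = 28 | 91 − 28 = 63 |
| 14 | 91 − 91 = 0 | 91 − 42 = 49 |
| 15 | 91 − 98 < 0, impossible | 91 − 49 = 42 |

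After a four-week wait (start on day 28), courses of 11 or more visits are cut off. After a six-week wait (day 42), courses of 9 or more are cut off. Patients already at half are correctly counted, so discharge is the more exposed outcome.

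**4. Mixing speed with completion.** The documents give no waits, attendance rate or discharge rate, so these are assumptions:

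- R uniform on 5-15
- lognormal wait with log-SD 0.5, median 6 weeks (control) v 4 weeks (video)
- 75-100% of weeks attended
- equal eventual half-completion of 0.66 × 0.73 = 48% (rates from section 1.1, where the chart review's own window is not given)
- discharge at the last recommended visit, with an eventual rate of 24% or 48%

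Observed rates come from 400,000 simulated patients per scenario. They are followed by the exact probability that the two-sided 5% chi-square test at 96 per arm favours the video.

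At 13 weeks, half-completion is 44.4 v 35.9% with full attendance. As a check by normal approximation, the pooled SE is √(0.4015 × 0.5985 × 2/96) = 0.0708, and Φ(0.085/0.0708 − 1.96) = Φ(−0.76) = 22%. At 75% attendance it is 38.7 v 29.0%, giving 29%.

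Trials declaring the video better (nominal 2.5%):

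| Review time | Half-completion | Discharge |
|---|---|---|
| All at 13 weeks | 22-29% | 11-29% |
| All at 17 weeks | 6-10% | 10-25% |
| All at 20 weeks | 4-5% | 7-17% |
| Spread evenly, 13-39 weeks | about 4% | 4-7% |
| All at 26 weeks | about 3% | 3-7% |
| All at 38 weeks | not tabulated | about 3% |

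At 13 weeks the review sees 80-92% (4-week wait) or 60-75% (6-week wait) of eventual half-completions. For eventual discharges it sees 28-46% or 18-30%.

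Sensitivity:

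- Log-SD 0.3-0.7, half-completion: 16-30% at 13 weeks, 3-13% at 17, 3-6% spread, 2-4% at 26.
- Log-SD 0.3-0.7, discharge: 9-35%, 10-25%, 4-8% and 2-9% at the same times.
- Median waits of 4 v 3 weeks: at 13 weeks, half-completion 5-8% and discharge 6-11%; with spread reviews, about 3-4% for both.
- A different wait model (exponential, means 6 v 4 weeks, all courses 15 visits, eventual 50% in both arms): observed half-completion, control v video, is 32 v 39% at 13 weeks, 46 v 48% with spread reviews and 50 v 50% at 39 weeks.

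**5. Lost power without any difference in waits.** Suppose early review captures a fraction f of eventual half-completers in both arms (f is assumed). By the two-proportion formula of step 1:

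| f | Rates compared | Power at 96 per arm | n per arm for 80% |
|---|---|---|---|
| 0.95 | 66.5 v 47.5% | 76.2% | 106 |
| 0.90 | 63.0 v 45.0% | 70.9% | 120 |
| 0.80 | 56.0 v 40.0% | 60.3% | 152 |

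**The case against.** **Worst-case timing.** The large figures need every chart to be opened near 13 weeks, while the plan makes three months a minimum and allows up to nine. With reviews spread over the whole range, the excess nearly vanishes, and moving from there to day 182 gains little: about 4% to about 3% for half-completion, 4-7% to 3-7% for discharge. This stands as a limit on size. It does not settle the matter, because a team that reviews every chart at three months also follows the plan exactly.

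**Assumed inputs.** Waits, attendance and the discharge rule are not in the documents, and a four-minute video may not shorten the median wait by two weeks. This also stands, and the 4 v 3 week results show how far the effect shrinks. The calendar limits in step 3 need none of these inputs.

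**Estimand.** Hypothesis 1 does not say eventual compliance. More patients having reached half by the review could be called a real effect of the video. That is arguable for a stated time point, but here no time point is stated, so neither reading can be claimed.

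**Short form.** The forms also omit UDI-6 and primary language, which section 2.6 analyses, so absence from form 4.5 does not prove a date will not be retrieved. Visits may be dated in the medical record, which would allow a common cut-off at abstraction. Fair, but the plan calls for no such cut-off, and the item list in section 1.4 has no review date either.

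**Conclusion.** The concern holds and should be fixed. Two of the five hypotheses, including the one that sets the sample size, rest on outcomes with no defined assessment time, and the listed data items would not allow an adjustment afterwards. That part rests on the text and the weekly schedule alone, and confidence in it is high.

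The size is conditional. With reviews clustered at three months and a two-week difference in median wait, the chance of a spurious finding for the video is roughly ten times nominal for half-completion and four to twelve times for discharge (22-29% and 11-29%, each against 2.5%). With late or evenly spread reviews it is small for half-completion and modest for discharge. The trial remains a valid randomized comparison; what is unclear is which quantity it compares.

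**What to change.** Replace the limits in section 1.4 and form 4.5 with one window for every participant. For example:

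> First visit, completed visits and discharge are counted up to and including day 182 (26 weeks) after referral. The chart is reviewed after that day, and later events are ignored.

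State in section 2.6 that the logistic models for half-completion and discharge refer to status on that day. Add the cut-off date to form 4.5 and use it as the Kaplan-Meier censoring date for never-attenders.

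Day 182 lies inside both existing limits. A 15-visit weekly course can finish by then if started by day 182 − 98 = 84, and reach half if started by day 182 − 49 = 133. If discharge matters as much as half-completion, a common cut-off just under nine months, such as day 266 (38 weeks), removes nearly all remaining truncation under the assumptions above.

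The cost is small. The last chart reviews fall about three months later than the current minimum with day 182 (182 − 91 = 91 days), or nearly six months later with day 266 (266 − 91 = 175 days). No extra visits, staff or patients are needed. Events after the cut-off are given up.

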#### **4.3. Patient information collected (in clinic)**

Circle one:      Control      Intervention (video)

Age \_\_\_\_\_      Vaginal Parity \_\_\_\_\_      BMI \_\_\_\_\_

Insurance type:      Private      Government sponsored      Combined      Other

Race      Caucasian      Black      Asian      Eastern European      Hispanic      Other

Urogynecologic diagnoses (circle):      SUI      UUI      MUI      Urgency-frequency Syndrome

Weak pelvic floor      Defecatory dysfunction      POP      Myofascial pain      Other

Stage of Prolapse      0      1      2      3      4      Not Assessed

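### No masked chart review is specified, and the plan does not say that the arm is withheld from the therapists who set the denominator of the powered endpoint.

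*Combined protocol and SAP*

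**What the plan says.** - **Endpoint collection.** Section 1.4 (Study Length) says that "medical record review will be performed to record therapy attendance, including date of first visit, number of visits recommended by the therapist", along with completed visits and discharge status. Section 2 (Follow-up) says that the chart will be monitored. Neither names the person who does this.
- **Where the arm is written.** The clinic form in Appendix 4.3 opens with an item to circle, Control or "Intervention (video"). The chart form in Appendix 4.5 has no arm field as printed. Its items include the recommended and completed visit counts and a yes/no item, "Discharged from PFPT practice (circle").
- **Who made the intervention.** In section 1.1 the practice states: "We designed and created a four minute patient education video". The same section says that physicians and pelvic floor physical therapists appear in it.
- **Masking.** Section 2.4 covers 1:1 block allocation and its timing. Section 2.5 codes data under an identification number for confidentiality. Section 2.6 describes no masked reading. The available text, which does not include Appendix 4.2, mentions no masking of patient, physician, therapist, chart reader or analyst.

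**The concern.** A woman cannot be masked to whether she watched a video. The protection left is to mask the person who reads the outcome and, as far as possible, the therapist who generates part of it. The plan provides for neither.

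This matters most for two items. Hypothesis 1, on which the study is powered, is a ratio whose denominator is a number chosen by the therapist. The plan does not say whether an initial or a revised recommendation counts. Hypothesis 4 rests on a discharge item that has no stated criterion. The date of the read is also loose: three months or more in section 1.4, under nine months in the heading of Appendix 4.5. If a chart is unclear, a reader who knows the arm has some discretion, and the practice has an interest in its own video. Any tilt would add directly to the measured effect.

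**Working it through.** **1. The plan's own figure.** Inputs from section 1.4: "With proposed sample sizes of 96 assigned to handout only and 96 assigned to handout and video intervention"; "specifically, 70% versus 50% compliance for the intervention and control groups, respectively"; "the criterion for significance (alpha) will be set at 0.05 and that the test will be 2-tailed". The stated result is that "the study will have power of 80% to yield a statistically significant result". The pooled-variance normal approximation gives 81.2%, and exact enumeration of the uncorrected chi-square test gives 80.9%. The stated power reproduces and is not in dispute.

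**2. Which items are exposed.**

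| Item on form 4.5 | Used for | Room for interpretation |
|---|---|---|
| Days to first visit | Hypotheses 2 and 3 | Little |
| Completed visits | Hypothesis 1, numerator | Little, once the reading date is fixed |
| Recommended visits | Hypothesis 1, denominator | Some: set by the therapist, may be revised |
| Discharged, yes/no | Hypothesis 4 | Some: no criterion given |

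**3. How sensitive the endpoint is to the denominator.** Section 1.1 gives a usual range of 5 to 15 visits. A woman who completes 4 visits meets the criterion if 5 to 8 were recommended and fails if 9 to 15 were.

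For a rough average, assume that recommended visits N are uniform on 5 to 15 and that a starter's completed visits are uniform on 1 to N. For each N, moving N by two visits changes the result for exactly one value of completed visits, so the share changed is 1/N. The average is (1/5 + 1/6 + … + 1/15)/11 = 1.235/11 = 11.2% of starters. At the 66% initiation rate in section 1.1 this is 0.66 × 11.2% = 7.4% of all women.

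**4. What a net tilt does to the error rate.** Assume no true effect, 96 per arm, a 50% base rate and the uncorrected two-sided chi-square test at 0.05, evaluated by enumeration. This stands in for the unadjusted logistic model of section 2.6.

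| Net tilt towards video | Women in 96 | Rejection rate |
|---|---|---|
| 0 points | 0 | 5.1% |
| 3 points | 2.9 | 7.1% |
| 5 points | 4.8 | 10.8% |

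With a base of 0.66 × 0.73 = 48.2% from section 1.1, the 3- and 5-point rates are the same to one decimal.

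**5. How much misreading such a tilt needs.** If only the video arm is affected, and always by two visits in the favourable direction, 3 points needs 3/7.4, about 40%, of its starters to be affected. Five points needs 5/7.4, about 67%. Eight points would need 8/7.4, about 108%, which is impossible.

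The uniform model also implies that 58% of starters complete at least half, against 73% in section 1.1. Reweighted to 73%, lowering every video-arm denominator by two changes 0.66 × 0.27 × 0.277 = 4.9% of women, where 0.277 is the average share of failing starters who then pass. Raising every control denominator by two changes 0.66 × 0.73 × 0.191 = 9.2%, where 0.191 is the average share of passing starters who then fail. Three points is therefore attainable under strong assumptions. Five is at or beyond the limit for the video arm alone and needs some opposite movement in the control arm.

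**The case against.** The strongest reply is that the gap is one of silence, and that copying a number from a chart leaves little room for bias. Much of this stands, and it rules out several stronger readings.

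- *The team that made the video reads the charts.* A reader might infer this for a single practice, but the reader is unnamed.
- *The arm is in front of the reader.* It is on form 4.3, not form 4.5, and nothing says that the two are kept together. Equally, nothing separates them. The coding in section 2.5 protects identity and does not conceal the arm.
- *Therapists know the arm.* No passage puts the arm in the medical record or has anyone tell a therapist. Section 1.1 does not say that the therapists in the video are the treating ones. The plan only fails to say that the arm is withheld.
- *Therapists decide discharge.* This is likely but not stated.
- *The error rate is inflated to a known level.* The tilts in step 4 are chosen inputs, not consequences of the design, and step 5 shows that the larger ones need widespread misreading.

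The reply does not remove the gap. The therapist sets the denominator, the arm is on a study form, and no step masks the later reading.

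**Conclusion.** The concern holds in a limited form. The plan specifies no masked chart review and does not say that the arm is kept from therapists. The exposure is mainly in hypotheses 1 and 4; hypotheses 2 and 3 rest on largely objective items. The size of any bias cannot be obtained from the documents. The figure of about 7% to 11% is an illustration for an assumed net tilt of 3 to 5 points with 96 per arm, and its upper end is demanding. It should not be read as evidence that bias will occur. Masked reading is worth adding because it costs almost nothing and is the main safeguard left when participants cannot be masked. The finding covers only the text available.

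**What to change.** 1. Remove the arm item from form 4.3 and hold the arm only in the randomisation log.
2. Complete form 4.5 by study number without the arm, and join the arm to the data only after all 4.5 forms are locked.
3. State in section 1.4 or 2.4 that study staff do not enter the arm in the medical record or tell the therapists.

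This takes one form edit and a short addition to the text. The same staff can do it, with no extra visits and no change in sample size. The costs are that the arm can no longer be looked up from the clinic form, and that masking stays imperfect: a reader may remember a woman, or she may tell her therapist. The first two steps protect the chart reading. The third gives only partial protection on the therapist's side.
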